#### Provider sample collection

Participants will attend a scheduled, standard of care visit with their provider either for screening of HR-HPV or for follow-up within 18-months of the positive HR-HPV test for a repeat pap smear, colposcopy, or loop electrosurgical excision procedure. The provider will be asked to collect an additional sample for the study, which will be shipped to a laboratory for HR-HPV analysis. Additionally, at this time the participant will be asked to obtain two "self-swabs". While in clinic, she will be administered swab device kits with verbal and written instructions.

We are using a commercially available menstrual pad. The menstrual pad is made of organic cotton and is today commercially available in convenient stores such as CVS and Walgreens. The only difference to a normal product is a small strip that is embedded beneath the first cotton layer. The strip consists of medical grade materials manufactured according to the ISO 13495 standard for medical devices. The core material in the strip is a proprietary paper-based sample receiving material from GE, namely a Whatman 903 collection paper. This is a commercially available product.

#### Follow-up

After we have received the sample collected by the participant and the provider, the subject will receive compensation.

# 5.0 STATISTICAL CONSIDERATIONS

#### 5.1 Outcome Measurements

Primary outcome is to compare the accuracy and percent analytic agreement of clinician and self-collected cervico-vaginal brush samples with Q-pad-collected menstrual blood for HR-HPV detection in women with and without previous positive HR-HPV results. The secondary outcome is to assess the ability to detect oncoproteins in Q-pad collected menstrual blood samples from women with ASCUS+ to determine the utility in cervical cancer/precancer detection and to test the utility of a low and high threshold HR-HPV reflex scheme to similarly increase the specificity of HR-HPV testing derived from menstrual blood. Neither outcome measures relate to safety.

#### 5.2 Analysis plan

We will record all data on an electronic tablet using REDCap electric data capture tools hosted at the Stanford Center for Clinical Informatics. 25 IBM SPSS Statistics, version 25.0 (IBM Corp., Armonk, N.Y., USA) will be used for data analysis. We will assess sociodemographic and clinical characteristics using descriptive statistics; if comparisons are needed, chi square tests or Mann-Whitney U tests will be used, where appropriate. We will assess the percent agreement of the binary outcome of HPV positive or negative on the menstrual blood sample analysis compared to the clinician swab and the self-swabs using Cohen's kappa.

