Menstrual blood is composed of three distinct body fluids: whole blood, vaginal fluid, and endometrial cells shed from the endometrial lining. While menstrual blood has been presumed to be virtually identical to whole blood, important differences exist and have been understudied. Studies from the 1980s found that menstrual fluid lacks factor X, pro-thrombin, and free thrombin. Proteomic and small-scale HPV detection studies have been recently published on menstrual blood, yet rigorous, larger-scale and implementation-level studies remain to be performed. In preliminary (unpublished) findings on HR-HPV screening with the Q-pad, we found that device detected HR-HPV using the GeneXpert POC test, and, anecdotally, women preferred this approach to self-collected and clinician-collected samples. We found favorable participation in community-based screening. Additionally, in rural, low-resource settings, DBS is easier to transport than slides, urine, or liquid-based cervico-vaginal samples, requires no refrigeration, and can potentially provide a "woman's physical" in a self-collected sample.

Our proposed study would be the first to rigorously examine the utility and feasibility of using menstrual blood collected by women for detection of HR-HPV DNA and HPV E6/E7 mRNA, using the Q-pad. We hypothesize that using self-collected menstrual blood from the Q-pad may be a more convenient, comfortable and cost-effective method for HR-HPV and E6/E7 screening, compared to currently implemented approaches, with high correlation to conventional HR-HPV testing. Our approach to screening may also allow for improved access to screening for cancer and precancer in the areas with the highest burden of disease, including unscreened women in the US and worldwide.

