#### 3.0 STUDY ENROLLMENT AND PARTICIPANT ELIGIBLITY

The participant population to be included in the study is menstruating women over the age of 18. There will be two groups: 1) menstruating women over the age of 18 who have a previous history of HR-HPV in the last 18 months and 2) menstruating women over the age of 18 who do not have a previous history of HR-HPV. We plan to recruit patients from Stanford research IT Starr cohort tool to identify patients who have had a positive

HR-HPV test in the past 18-months. In addition, we also plan to recruit women without previous history of HR-HPV, who present in clinic for a cervical cancer screening test as part of their standard of care well woman visit.

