# For participants with no prior HR-HPV history:

We plan to recruit patients from Stanford Gynecology clinic. We will review the clinic schedule for patients presenting to the clinic for their routine well woman visit with cervical cancer screening. Their provider will approach the patient during that clinic visit to assess if the patient would be willing to participate in the project. If the patient agrees, then research staff will present the project in detail to the patient and obtain consent. At the time of the routine cervical cancer screening, additional study swabs will be collected. Prior to discharge, research staff will show the subject how to use the Q-pads and the vaginal swabs to ensure subjects fully understand the process. We do not anticipate any screen failures.

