#### 3.3 Enrollment

The target number of subjects at our gynecology clinic is 250 patients with or without previous HR-HPV diagnoses. We expect to complete this study within 12 months.

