# **APPENDIX B: Protocol Summary of Changes**

Any administrative changes to the protocol including spelling corrections, minor clarifications, renumbering, and reformatting are not summarized in the following table.

Section	Change to Protocol	Rationale
Title Page	Date and version # changed	Changed due to this revision
Specific Study Aims	Added samples from women with no previous history of HR-HPV to specific aim #1	The study team assessed the funding timeline and the current sample (n=70) and the goal of n=250 and identified the need to expand the inclusion criteria. By including those without a history of HPV, we are able to better assess specificity and sensitivity. One challenge our team has faced is that far less women menstruate regularly than anticipated—this is largely due to contraceptive use.
Study Enrollment and Participant Eligibility	Created two groups for study enrollment to include women with no previous history of HR-HPV	To collect as much information as possible given funding timeline restraints. See above.
Study Enrollment and Participant Eligibility	Changed age restrictions to include for women over 45 years of age.	To allow for menstruating women over the age of 45 to participate. Upon review of our age eligibility, we saw no reason to exclude those over 45 years of age who menstruate. Screening still occurs in this population.
Material and Methods	Changed methods to include approaching women presenting to clinic for repeat cervical cancer screening with or without a history of HR-HPV.	To expand enrollment.
Statistical Considerations	These changes will not impact the statistical methods.	To accommodate expanded enrollment.

Data Management	Added section 6.4	To provide clarity on
Considerations		amendment approval.

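### Section 5.2 does not say whether agreement is reported by HR-HPV history group; a crude kappa over all 250 women would mix within-group agreement with the difference in positivity between the groups

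*Combined protocol and SAP*

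**What the plan says.** Section 3.0 sets up two groups: "menstruating women over the age of 18 who have a previous history of HR-HPV in the last 18 months", and menstruating women without such a history. Section 3.1 draws the first group from women returning for follow-up of a positive test. It draws the second from "patients presenting to the clinic for their routine well woman visit with cervical cancer screening". Section 5.1 puts both into the primary outcome, "for HR-HPV detection in women with and without previous positive HR-HPV results".

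Section 3.3 sets one target with no split: "The target number of subjects at our gynecology clinic is 250 patients with or without previous HR-HPV diagnoses".

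The whole primary analysis is one sentence in 5.2: "We will assess the percent agreement of the binary outcome of HPV positive or negative on the menstrual blood sample analysis", compared with the clinician swab and with the self-swabs by Cohen's kappa. It gives no group term, stratification or per-group estimate. It also gives no estimator of sensitivity or specificity, although 5.1 makes accuracy part of the primary outcome. Appendix B records the position taken when the second group was added: "These changes will not impact the statistical methods".

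The intended use in 2.0 is wider access to screening, "including unscreened women in the US and worldwide".

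**The concern.** Kappa depends on the proportion positive as well as on how well two specimens agree. If one group is mostly positive and the other mostly negative, both specimens will separate the groups, and a table over everyone counts that separation as agreement beyond chance. The single figure then sits above the average of what holds inside the groups, and it shifts with how many women of each kind enrol.

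The consequence falls on the use the study is meant to support. Women at a routine screening visit are the closest match to it, but they are likely to contribute few of the positives. Weak pad detection in them could be hidden by good detection in women already under follow-up.

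**Working it through.** **The plan's own figure.** Section 5.3 reaches 250 by 10,000 visits × 0.05 prevalence × 0.50 recruitment = 250. That is a count of positive women. Section 3.3 now applies 250 to both groups together. No group split is given, and neither is current positivity in the history group, whose follow-up visit may fall up to 18 months after the positive test.

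**Inputs.** From the documents: 250 women in total; 70 enrolled when the second group was added, leaving 180; and 5% prevalence (5.3, which adds that the local rate is probably higher). Assumed, because the documents give no figure: the group split, positivity in the history group, any well-woman prevalence other than 5%, and pad sensitivity (Se) and specificity (Sp) against the clinician sample.

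**Formulas.** For a group of n women with proportion positive p, the expected cells are a = n·p·Se (both positive), b = n(1−p)(1−Sp), c = n·p(1−Se), d = n(1−p)Sp. Then Po = (a+d)/n, Pe = [(a+b)(a+c) + (c+d)(b+d)]/n², and kappa = (Po−Pe)/(1−Pe). The pooled table adds the cells of the two groups.

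**Wide gap, 125/125, Sp 95%, Se 90% in the history group and 60% in the other.**

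| Table | a | b | c | d | Po | Pe | kappa |
|---|---|---|---|---|---|---|---|
| History, 60% positive | 67.5 | 2.5 | 7.5 | 47.5 | 0.920 | 0.512 | 0.84 |
| No history, 10% | 7.5 | 5.625 | 5 | 106.875 | 0.915 | 0.816 | 0.54 |
| Pooled, 60% v 10% | 75 | 8.125 | 12.5 | 154.375 | 0.9175 | 0.550 | 0.82 |
| No history, 5% | 3.75 | 5.9375 | 2.5 | 112.8125 | 0.9325 | 0.880 | 0.44 |
| Pooled, 60% v 5% | 71.25 | 8.4375 | 10 | 160.3125 | 0.926 | 0.563 | 0.83 |

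- The mean of the two group kappas is 0.69 at 10% and 0.64 at 5%, so the pooled value is 0.13 and 0.19 too high as a summary of them.
- Pooled sensitivity is 75/87.5 = 86% and 71.25/81.25 = 88%, against 60% in the no-history group.
- The history group supplies 75 of 87.5 reference positives (86%) at 10%, but only 50 of 162.5 reference negatives (31%).

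**Enrolment mix.** At 60% v 10% with the same pad performance, pooled kappa is 0.84 with a 180/70 split (history/no history) and 0.77 with 70/180.

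**Equal pad performance.** With Se 85% in both groups, 125/125 and 60% v 10%, the group kappas are 0.78 and 0.71 and the pooled kappa is 0.81, above both.

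**Small gap.** With 40% v 15%, 70/180, Se 85% in both groups and Sp 95%, the group kappas are 0.81 and 0.76 and the pooled kappa is 0.79. The size-weighted mean is 0.77, so the excess is 0.02. The history group supplies 28 of 55 positives, about half.

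**Range.** The grid had 108 scenarios: history group of 70, 125 or 180; positivity 30–90% against 5–15%; Se/Sp of 0.80/0.90, 0.90/0.95 or 0.95/0.98, equal in both groups. Pooled kappa exceeded the size-weighted mean of the group kappas in all 108, by 0.004 to 0.31. It was above both group values in 65 and between them in 43. The history group supplied 44–98% of positives and 4–68% of negatives.

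**Group difference alone.** Take 125/125, 50% v 5%, and agreement at chance inside each group (both kappas 0). Then Po = (31.5625 + 144.0625)/250 = 0.7025, Pe = 0.275² + 0.725² = 0.60125, and pooled kappa = 0.10125/0.39875 = 0.25.

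**The case against.** The strongest reply is that 5.2 never says the groups will be combined. Naming both populations in 5.1 is compatible with reporting each, so pooling is inferred from silence. That stands. It leaves open a choice that changes the headline result, in the only analysis text there is.

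Four stronger readings are tempting, and the documents do not support them.

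- *Pooled kappa exceeds the kappa in both groups.* Sometimes it does. In the wide-gap scenarios above it lies between them, as in 43 of the 108.
- *Pooled accuracy mostly reflects known positives.* This holds for sensitivity when the gap in positivity is wide. Specificity draws on reference negatives, most of which usually come from the no-history group, and 5.2 specifies no accuracy estimator.
- *Percent agreement is inflated too.* It is not. It is a size-weighted average and always lies between the groups: 92.0% and 91.5% by group, 91.75% pooled, at 60% v 10%.
- *The Appendix B entry is itself the error.* It is a change log. It matters only as confirmation that 5.2 was not revisited. The same log says that women without a history were added deliberately, to improve the assessment of sensitivity and specificity.

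It is also fair to say that group kappas vary with prevalence, so kappa by group is not enough alone. Splitting the sample also leaves few positives among the screening women.

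**Conclusion.** The concern holds in this form: the primary question covers two groups with different expected positivity, and the stated analysis has no group term. Run as written over 250 women, crude kappa would overstate average within-group agreement by an amount that depends on the positivity gap and the enrolment split, neither of which is planned or stated. Pooled sensitivity would mostly reflect the history group when the gap is wide. Specificity and percent agreement would follow the enrolment mix.

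The size is illustrative. It runs from about 0.02 in kappa at 40% v 15% (70/180, Se 85% in both groups) to 0.13–0.19 at 60% v 5–10% (125/125, Se 90% v 60%). Only the 5% and the total of 250 come from the documents. It should be fixed because the correction is cheap and the headline result depends on it. It does not show that the pad performs badly in either group, or that the sponsor intends to pool.

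**What to change.** In 5.2, for the pad against the clinician swab and separately against the self-swabs, report positive percent agreement, negative percent agreement and kappa with 95% confidence intervals within each HR-HPV history group. Give any pooled kappa only as a secondary, group-stratified summary. Base statements about screening on the no-history group.

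Define that group one way throughout. Sections 3.0 and 3.1 require no previous history, whereas 3.2 requires no positive test in the last 18 months. Record the group as an analysis variable; the eligibility items in Appendix A do not ask about HR-HPV history.

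The cost is mostly wording, plus one recorded variable. The real downside is precision. At the protocol's 5%, 125 no-history women give about 6 positives (125 × 0.05 = 6.25) and 180 give 9. With 8 of 9 detected, the 95% Wilson interval is 57–98%. The plan should state this, and the precision statement in 5.3 should not be claimed for each group.

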#### 1.0 SPECIFIC STUDY AIMS

Specific Aim #1: To compare the accuracy and percent analytic agreement of clinicianand self-collected cervico-vaginal brush samples with Q-pad-collected menstrual blood for HR-HPV detection in HR-HPV positive women and women with no previous history of HR-HPV.

Specific Aim #2: 2.1: To assess the ability to detect oncoproteins in Q-pad collected menstrual blood samples from women with ASCUS+ to determine the utility in cervical cancer/precancer detection and 2.2: to test the utility of a low and high threshold HR-HPV reflex scheme to similarly increase the specificity of HR-HPV testing derived from menstrual blood.

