## 4.0 MATERIAL AND METHODS

#### Pre-procedure

Pre-procedure meetings will be performed with the subjects individually where the process will be discussed and two designated menstrual pads (pad 1 and pad 2) and two pouches (pouch 1 and pouch 2) will be dispensed. We will instruct the subjects on how to use the pads and go through the consent form with them and answer any questions they might have.

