# 5.3 Sample size

We chose a convenience sample of 250 women based on the following: Stanford Gynecology clinic has approximately 10,000 unique visits per year. A "worst case" HPV prevalence rate of 5% (similar to rural Thailand), yields approximately 500 positives for HR-HPV per year and recruitment experiences from similar studies indicates a recruitment rate of 50% of the positives for something like this is feasible. In fact, the local HPV prevalence rate in our catchment area is likely much higher than 5%. Also 250 women would allow for adequate precision of 95% relative to agreement of the menstrual specimen with the lab-generated HPV result (alpha =.001, beta=.10).

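### For the primary comparison, section 5.2 names only Cohen's kappa, so the accuracy half of the primary outcome has no estimator and no designated reference

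*Combined protocol and SAP*

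**What the plan says.** Aim 1 (section 1.0) is "To compare the accuracy and percent analytic agreement" of clinician- and self-collected samples with Q-pad menstrual blood. Section 5.1 repeats both parts as the primary outcome: to "compare the accuracy and percent analytic agreement of clinician and self-collected" samples with the Q-pad, in women with and without earlier positive results.

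Section 5.2 gives this outcome one sentence. Percent agreement on the positive/negative result is to be assessed on the "menstrual blood sample analysis compared to the clinician swab and the self-swabs using Cohen's kappa". The other methods in 5.2 (descriptive statistics, chi-square, Mann-Whitney) are for sociodemographic and clinical characteristics.

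Section 5.3 justifies 250 women partly by precision for "agreement of the menstrual specimen with the lab-generated HPV result", without saying which sample produces that result. Specificity appears in section 5.1 only for the secondary reflex scheme. Sections 5.1 to 5.3 plan no sensitivity, specificity, positive or negative agreement, or confidence interval for the primary outcome.

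The change summary in Appendix B gives as a reason for adding women without a history: "By including those without a history of HPV, we are able to better assess specificity and sensitivity".

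**The concern.** An accuracy objective needs a reference result and an estimator that separates the two kinds of error. The plan has neither. The two comparators stand side by side without ranking, and 5.3 adds a third term whose source is not identified. The one statistic named does not measure percent agreement either, because it subtracts the agreement expected by chance, which depends on how many women are positive.

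For a screening specimen, the main question is whether it misses infections that the clinician sample finds. A report that followed 5.2 to the letter could give a kappa and leave that question unanswered. With no reference fixed in advance, it could also be chosen after the results are known.

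**Working it through.** **The plan's own figure.** Recruitment arithmetic in 5.3: 10,000 visits × 5% × 50% = 250. The accompanying precision statement (95%, alpha .001, beta .10) cannot be reproduced, because no null value, expected kappa, proportion positive or sidedness is given. The point below does not depend on it.

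**Inputs.** n = 250 is from 5.3. All cell counts are assumed, with 12 discordant pairs throughout, so overall agreement is always 238/250 = 95.2%.

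**Formulas.** Write each table as a = both positive, b = reference positive/pad negative (missed), c = reference negative/pad positive (false positive), d = both negative.

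- Overall agreement: po = (a + d)/n
- Chance agreement: pe = [(a + b)(a + c) + (c + d)(b + d)]/n²
- Kappa = (po − pe)/(1 − pe)
- Positive agreement = a/(a + b); negative agreement = d/(c + d)

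**Step 1: direction of error.**

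- (20, 10, 2, 218): pe = (30 × 22 + 220 × 228)/62,500 = 0.813; kappa = (0.952 − 0.813)/(1 − 0.813) = 0.74. Positive agreement 20/30 = 67%, negative 218/220 = 99%.
- (20, 2, 10, 218): the products are the same, so pe and kappa are unchanged at 0.74. Positive agreement 20/22 = 91%, negative 218/228 = 96%.

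Swapping b and c exchanges the roles of test and reference, and kappa does not register it. The swap also moves the number of reference positives from 30 to 22. With reference positives held at 25, kappa does move: 0.66 for (13, 12, 0, 225) and 0.78 for (25, 0, 12, 213). Kappa therefore sometimes shifts with the direction of error, but its value does not tell the reader which direction it was.

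**Step 2: proportion positive.** Agreement stays at 95.2%.

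| Reference positive | Missed / false positive | pe | Kappa | Positive agreement |
|---|---|---|---|---|
| 125 (50%) | 12 / 0 | 0.500 | 0.90 | 90% |
| 125 (50%) | 0 / 12 | 0.500 | 0.90 | 100% |
| 12 (4.8%) | 12 / 0 | 0.952 | 0.00 | 0% |
| 12 (4.8%) | 6 / 6 | 0.909 | 0.48 | 50% |
| 12 (4.8%) | 0 / 12 | 0.865 | 0.64 | 100% |

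One value of percent agreement is thus compatible with any of these kappas, from 0.00 to 0.90.

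**Step 3: precision of the replacement.** Appendix B gives 70 women enrolled when the no-history group was added. If all later women have no history, that leaves 250 − 70 = 180. At 5% positive, 180 × 0.05 = 9 positives. For an assumed 8 of 9 detected, the Wilson 95% interval, [p + z²/2n ± z√(p(1 − p)/n + z²/4n²)]/(1 + z²/n) with n the number of positives and z = 1.96, is 57% to 98%. Over the whole sample, if 60% of the 70 history women are positive (42), there are 42 + 9 = 51 positives; an assumed 44/51 gives 74% to 93%.

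**The case against.** The strongest reply is that nothing is lost. Kappa needs the 2×2 table, and every measure asked for here can be read from it. Section 5.2 may also mean that percent agreement will be reported with kappa beside it. Both points are fair, and they make this a gap in pre-specification rather than in data collection. They do not fill it: no sentence commits the study to an accuracy measure or a reference.

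A second reply is that discordance is not always Q-pad error. Section 4.0 lets pads be used in the cycle before or after the visit, and the visit may be for an excision procedure. This stands, and it affects how any agreement measure is interpreted, kappa included.

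Third, a reader might infer that a combined kappa would hide poor performance in women without a history. The documents do not establish this. It depends on positivity and agreement by group, which they do not give, and a lower kappa in a low-positivity group can arise with an equally good device. Section 5.1 does not expressly require results by group. Overall positive agreement could be dominated by the history group in the same way: 42 of 51 positives in the illustration above.

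Finally, a reader might set the Appendix B rationale against 5.2 as a contradiction. Appendix B is a summary of changes, so it shows intent and supports the point without proving it. Sections 1.0, 5.1 and 5.2 are sufficient.

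**Conclusion.** The point holds for the primary comparison. Accuracy is half of the stated primary outcome and has neither an estimator nor a designated reference; percent agreement is tied to a statistic that measures something else. It should be fixed before analysis.

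The size shown, positive agreement of 67% or 91% behind one kappa of 0.74, and kappa from 0.00 to 0.90 at one level of agreement, comes from assumed counts. It shows what kappa can conceal and does not predict this study's results. Kappa's symmetry and its dependence on the proportion positive need no assumption.

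Two broader readings go too far. Section 5.2 does plan other statistics, though for participant characteristics. And the study would still hold the data to show missed infections; what is absent is a commitment to report them against a named reference.

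**What to change.** In section 5.2:

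- Designate the clinician-collected study sample as the reference for accuracy. It is already a named comparator and is taken at the study visit, whereas an earlier positive result may be up to 18 months old.
- Make positive and negative percent agreement (sensitivity and specificity relative to that sample) and overall percent agreement of the Q-pad the primary estimates, each with a 95% CI.
- Give the same agreement measures against the self-swabs.
- Report overall and, descriptively, by HR-HPV history group.
- Keep kappa as a secondary statistic.
- State that, because pads may be used in the cycle before or after the visit, some discordance may reflect real change.

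The cost is a protocol modification that needs IRB approval before it is implemented (section 6.4). No new samples or visits are needed. The drawback is a visibly wide interval for positive agreement in women without a history, as the 57% to 98% example shows. That imprecision exists whichever statistic is reported.
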